9.3 Concomitant medications

No other antidiarrheals will be allowed while on study treatment with colesevelam to evaluate efficacy accurately. If the diarrhea is worsening while on colesevelam, the patient will be

taken off study and can then start other anti-diarrheal medications. Similarly, if there is no sign of improvement after start of colesevelam despite dose escalation by 2 weeks, the patient will be taken off study and is allowed to start other anti-diarrheal medications.

Orally administered drugs that have not been tested for interaction with colesevelam, especially those with a narrow therapeutic index, should be administered at least 4 hours prior to colesevelam. Therefore, lenalidomide should be spaced out from colesevelam by 4 hours at least. In addition, the physician should monitor drug levels of the co-administered drugs. Medications with known drug interactions are listed under section 5.0 page 11.

10.0 EVALUATION DURING TREATMENT/INTERVENTION

10.1 Physical examination

A complete physical examination will be performed during screening and at the end of trial (12 weeks +/-7 days).

Physical exam will include:

- Abdominal examination
- Weight
- Height (at screening only)
- ECOG performance status

Abnormal physical examination findings during screening will be captured as medical history. Abnormal physical examination findings observed after signing of the informed consent will be recorded as adverse events (AEs).

10.2 Laboratory assessment

Laboratory assessment will include:

- Complete blood count with differential count
- Comprehensive metabolic panel: sodium, potassium, chloride, carbon dioxide, serum creatinine, glucose, blood urea nitrogen (BUN), EGFR, albumin, calcium, magnesium, phosphorus, alkaline phosphatase, ALT, AST, total bilirubin, direct bilirubin, uric acid, LDH, total protein
- Serum protein electrophoresis (SPEP) and serum immunofixation to assess for presence and quantity of monoclonal protein (M-protein)
- Serum free light chain studies
- Quantitative immunoglobulins

Hematology and chemistry panels will be performed during screening, at 4 weeks (+/-7 days), and at the end of trial (12 weeks +/-7 days).

10.4 Diarrhea assessments (primary endpoint)

Diarrhea assessments using the CTCAE scale will be performed at baseline (day 1 of colesevelam), at 1 week (+/- 2 days), 2 weeks (+/- 2 days), 4 weeks (+/- 7 days), and at 12

weeks (+/- 7 days). The assessment on week 1, 2, and 4 can be carried out as a telephone call by the treating physician or research nurse for reasons of convenience. In this event, the information regarding response will be collected over the phone and questionnaires will be handed in or sent to MSK.

Frequency and consistency of diarrhea/bowel movements will be recorded using a diarrhea questionnaire (Appendix 2). This will be used to grade the diarrhea according to the CTCAE scale (CTCAE, see section 8.0, page 15).¹⁴

10.5 Symptom and diet assessments (secondary endpoints)

GI symptoms will be assessed at each follow-up (baseline; day 1 of colesevelam), at 1 week (+/- 2 days), 2 weeks (+/- 2 days), 4 weeks (+/- 7 days), and at 12 weeks (+/- 7 days) and will be instructed to fill in the GI oriented PRO-CTCAE questionnaire. The PRO-CTCAE for Gastrointestinal Symptoms is a 10-item multiple choice questionnaire using a 5-point Likert-type response format (Appendix 4). There is no composite score for this instrument. All items in this questionnaire will be analyzed individually.

Diet will be recorded using a questionnaire for dietary intake at set time points during the study (Appendix 5). In the diet questionnaire, patients will record their dietary intake at baseline and at the follow up at week 1, 2, 4, and 12 after starting colesevelam. We will record dietary intake and ask whether the patients have changed their diet as a results of the diarrhea and/or lenalidomide or colsevelam treatment.

Consistency of bowel movements will be graded using the Bristol Stool Form Scale which was developed for patient use.³ Bristol Stool Form Scale categorizes stools into one of seven types based on stool consistency (Appendix 3).

These questionnaires together take between 10 and 20 minutes to complete. These instruments will be given to the patient at the start of the study and will be handed in at clinical visits or can be sent to MSK in the event that visits are replaced by a phone call (see section 4.2).

10.6 Correlative analyses: Pharmacokinetic studies

Blood samples will be collected from up to 15 subjects for determination of plasma concentrations of lenalidomide while on colesevelam the following time points:

- Pre- and 2 hours post the 1st dose of colesevelam considered day 1
- Pre- and 2 hours post the colesevelam dose on day 8 (± 2 days) of colesevelam

10.7 Correlative analyses: Gut microbiota and bile acid analyses

Stool samples will be collected from all patients at baseline and after 12 weeks of colesevelam therapy.

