4.0 OVERVIEW OF STUDY DESIGN/INTERVENTION

4.1 Design

This is a single institution, single arm, open label phase II trial to evaluate the efficacy of colesevelam for myeloma patients on lenalidomide maintenance who experience grade 1 or more diarrhea. Patients will be given colesevelam at a starting dose of 2 tablets (2 x 625 mg) which can be increased to up to 6 tablets per day depending on efficacy and tolerability, see dose adjustment schedule section 9.2, page 16. Patients can continue on the study until unacceptable toxicity, diarrhea that remains grade 1 or higher at week 4, worsening of diarrhea at any point, or end of study (12 weeks), whichever comes first. Each patient will be followed for a total 12 weeks.

The primary endpoint of this study is improvement of diarrhea. Response is defined as improvement by at least 1 grade according to CTCAE version 5.0 (see page 15) or returns to patients baseline when receiving colesevelam. A total of 25 patients will accrue on the study in a Simon's two-stage minimax design. In the first stage of the study, 16 patients will accrue. If 1 or fewer patients have a reduction in diarrhea severity, the study will stop due to a lack of efficacy; otherwise, an additional 9 patients will accrue. We estimate that the accrual to the study will be approximately two patients per month. The study is expected to be completed in approximately two years.

A diarrhea diary will be filled out by patients to capture frequency and consistency of bowel movements. GI symptoms will be assessed using the GI oriented PRO-CTCAE questions. Diet will be recorded at several time points to assess changes in dietary intake prior to and while on colesevelam. Stool consistency will be assessed using the Bristol Stool Form Scale. Correlative studies include pharmacokinetic (PK) evaluation of lenalidomide as well as collection of stool for studies of the GI microbiome.

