4.2 Intervention

All patients should be on maintenance single agent lenalidomide and experiencing grade 1 or higher diarrhea according to the CTCAE grading system. For treatment with colesevelam, the starting dose will be 1250 mg (2 x 625 mg) with food which can be increased to 6 tablets max per day based on efficacy and tolerability. Coleveselam should not be taken within 4 hours before or after lenalidomide and other interacting medications. All participants will be given a pill diary to record intake of colesevelam (Appendix 1). The effect of colesevelam on lenalidomide-associated diarrhea will be evaluated after 1, 2, 4, 12 weeks after start of treatment. If the diarrhea does not respond to the starting dose of colesevelam, the dose can be increased every 2 days to 2 tablets two times per day (2 x 625 mg BID) and later to 3 tablets two times per day (3 x 625 mg BID). The colesevelam dose can be decrease to 1 tablet per day if there has been improvement of diarrhea but emergence of side effects. Treatment with colesevelam will continue until drug-related toxicity, diarrhea that remains grade 1 or higher at week 2 despite dose elevations, or if worsening diarrhea occurs, or up to 12 weeks on study.

Patients will be evaluated by their physician and/or research nurse at baseline, after 1 week (+/- 2 days), after 2 weeks (+/- 2 days), after 4 weeks (+/- 7 days), and 12 weeks (+/- 7 days) for efficacy, toxicity, and compliance. The evaluations after 1, 2, and 4 weeks will preferably as office visits but can be replaced by telephone calls for sake of convenience.

Pharmacokinetics will be assessed in a subset of patients (up to 15 patients) at baseline and 8 days after start of colesevelam. All patients will be asked to participate in the PK studies and the first 15 who consent to this correlative part will be included. Research stool samples will be collected for all study participants at baseline and after 12 weeks of study.

Patients that repond to colesevelam can continue on the drug after the 12 weeks of study treatment. Coverage for colesevelam costs after the 12 weeks will not be covered by the trial but will go through patient's insurance.

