9.2 Dose adjustments

Colesevelam dosing can be adjusted based on tolerability and efficacy using Table 3. The dose of colesevelam can be increase or decreased at the invesitgator's discretion based on tolerability at any timepoint as long as changes and reason are documented. If Revlimid is held, colesevelam can be held at the same time.

Table 3. Dose levels and escalation/de-escalation for colesevelam

Dose level	Dosing of Colesevelam	Dose adjustment		
0	1250 mg (2 tablets) daily	Starting dose		
1	1250 mg (2 tablets)	Increase if diarrhea remains grade 1 or		
	twice daily	higher after 2 days on each dose level		
2	1875 mg (3 tablets)	Increase if diarrhea remains grade 1 or		
	twice daily	higher after 2 days on each dose level		
-1	625 mg daily	Decrease if improvement of diarrhea		
		but emergence of side effects		

Indications for discontinuation of study medication:

- If patients cannot tolerate dose level -1 then patients should discontinue treatment and come off study
- If patient has worsening of diarrhea within the first week after starting colesevelam, they should discontinue treatment and come off study
- If the diarrhea remains grade 1 or higher after 2 weeks of treatment

The investigator may *consider* withdrawing patients from the study for any of the following reasons:

- Side effects from colesevelam
- If there is protocol violation
- Non-compliance
- Administrative reasons
- Failure to return for follow-up

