10.10 Table 4. Overview of time points for sampling and clinical assessment

	Baseline	Cycle 1 Day 1 (Within 14 days of baseline)	Cycle 1 Day 8 (+/-7 days)	Cycle 1 Day 15 (+/-7 days)	4 weeks/ End of Cycle 1 (+/- 14 days)	12 weeks / End of Cycle 3 (+/- 21 days)
MD/RN assessment	Visit		Visit or telephone assessment	Visit or telephone assessment	Visit or telephone assessment	Visit
Stool studies GI pathogens ^a	Xa					
Triglycerides	X					
CBC	X					X
Comp	X					X
SPEP, IFE and FLC	X					X
Stool Diary (response assessment) and Bristol Stool Scale ^b	Х		X	х	Х	Х
PRO-CTCAE	X		X	Х	Х	Х
Nutritional Survey ^c						Х
PK studies ^d		Χq	Xq			
Research stool samples ^e	Х					X

- a. Stool studies for GI pathogens should be collected prior to starting colesevelam but do not need to be resulted prior to starting Day 1 dose of colesevelam, unless infection is suspsected by the treating investigator.
- b. Response assessments (Stool diaries) will be done at Cycle 1 Day 8, Cycle 1 Day 15, end of Cycle 1 (week 4) and end of Cycle 3 (week 12). If diarrhea does not improve by at least 1 grade from baseline (using CTCAE version 5.0) or to patient's baseline bowel pattern by the end of Cycle 1 they will be removed from study.
- c. Patients will complete one nutrtional survey ("Food and Activitity Questionaire" survey will be used) and return at week 12 visit.

- d. Lenalidomide pharmacokinetics will be assessed in up to 15 patients to assess possible drug interactions between lenalidomide and colesevelam. In these patients, a blood sample will be drawn pre- and 2 hours post the first colesevelam dose (day 1), as well as pre- and 2 hours post colesevelam on day 8 after initiation of colesevelam.
- e. Research stool samples will be collected at baseline and after 12 weeks of treatment for microbiota and bile acid studies.

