13.0 CRITERIA FOR REMOVAL FROM STUDY

Patients will be informed that they have the right to withdraw from the study at any time for any reason, without prejudice to their medical care.

The investigator is *required* to withdraw patients from the study for any of the following reasons:

- If at any time a patient develops unacceptable toxicity from colesevelam
- General or specific changes in the patient's condition unacceptable for further treatment in the judgment of the investigator

• If there is no resolution of diarrhea to grade 0 at 2 weeks after the dose has been increased to dose level 2

The investigator may *consider* withdrawing patients from the study for any of the following reasons:

- Side effects from colesevelam
- If there is protocol violation
- Non-compliance
- Administrative reasons
- Failure to return for follow-up

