the diarrhea responds to colesevelam. The proportion of patients who have had a change in their diet due to diarrhea, and the proportion who had a diet change due to either lenalidomide or colesevelam will be reported

- Patient diarrhea will be further summarized during the study period using the Bristol Stool Form Scale. The scale has seven types of stool consistency. The proportion of patients with improvements in stool consistency from baseline to weeks 1, 2, 4, and 12 will be calculated along with a 95% exact confidence interval.
- The proportion of patients with sustained response by week 12 (end of study) will be calculated with a 95% exact confidence interval. This is calculated as the proportion of patients who have grade 0 diarrhea at week 12 among patients who achieved grade 0 diarrhea by the week 4 assessment.

Correlative studies

Lenalidomide pharmacokinetics while on colesevelam will be described in up to 15 patients treated on this study; the changes from baseline will be reported.

Stool samples will be analyzed for changes in gut microbiota that take place before and after 12 week of colesevelam treatment. Changes in alpha diversity will be summarized using average change in the Inverse Simpson index. Microbial ecology and metagenomic analysis will be performed to describe changes in gut microbiota throughout the study.

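### Research stool is planned from all patients at baseline and week 12, but patients who do not improve leave at about week 2 or 4 with no sample at removal, so the microbiota change will describe only those retained to week 12

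*Combined protocol and SAP*

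**What the plan says.** **Sampling.** There are two research stool time points. Section 10.7 reads "Stool samples will be collected from all patients at baseline and after 12 weeks of colesevelam therapy", and section 4.2 reads "Research stool samples will be collected for all study participants at baseline and after 12 weeks of study". Section 8.7 agrees, and section 1.0 and Table 4 footnote e give the same two times. Section 8.3, however, lists the microbiota sample as optional.

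**Analysis.** Section 14.0 plans: "Changes in alpha diversity will be summarized using average change in the Inverse Simpson index". It gives no rule for a missing second sample, does not restrict the population and does not split by response. Section 8.7 leaves bile acid measurement as something that may be explored.

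**Removal.** Patients who do not do well are stopped early, under rules that differ:

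- Section 4.1 ends participation for "diarrhea that remains grade 1 or higher at week 4, worsening of diarrhea at any point".
- Section 9.2 lists as a reason to stop study medication: "If the diarrhea remains grade 1 or higher after 2 weeks of treatment". Sections 1.0 and 4.2 also use grade 1 or higher at week 2.
- Section 9.1 stops treatment for diarrhea that is unimproved at 2 weeks despite a higher dose.
- Section 9.3 takes a patient off study "if there is no sign of improvement after start of colesevelam despite dose escalation by 2 weeks" and then permits other antidiarrheals.
- Table 4 footnote b: patients without a one-grade improvement, or a return to their own bowel pattern, "by the end of Cycle 1 they will be removed from study".
- Section 13.0 requires withdrawal: "If there is no resolution of diarrhea to grade 0 at 2 weeks after the dose has been increased to dose level 2".

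**The concern.** The sampling sections promise a pair of samples from everyone. The removal rules mean that a patient who does not improve is no longer on colesevelam at week 12 and cannot supply the second sample. Whether the pair exists is then decided largely by the trial's own outcome, so the missing pairs are not missing at random.

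Two things are at stake. First, an average change reported without a label would be read as describing the enrolled group, when it describes those who stayed. Second, the trial's rationale is mechanistic: the case series in section 3.0 found bile acid malabsorption in 10 of 12 patients (9 severe, 1 mild). A natural correlative question is whether stool composition moves differently on drug in patients who respond and patients who do not. As scheduled, patients removed for non-response contribute nothing to that comparison, and a sample not taken at removal cannot be recovered later.

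**Working it through.** **Step 1: the design figures reproduce.** The stool correlative has no sample size of its own; it inherits the two-stage design in section 14.0. The inputs are 16 then 9 patients, stop at 1 or fewer responders of 16, promising if more than 4 of 25, response rates of 10% and 30%, and both errors 0.10. Exact binomial calculation gives type I error 0.0951 and power 0.9030. A full search returns the same design as the minimax solution, with N = 25.

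**Step 2: does any removal rule leave non-improving patients in place at week 12?**

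| Section | Time | Threshold for leaving |
|---|---|---|
| 4.1 | week 4 (worsening: any time) | grade 1 or higher |
| 1.0, 4.2, 9.2 | week 2 | grade 1 or higher |
| 9.1, 9.3 | week 2 | no improvement |
| Table 4, footnote b | week 4 | less than one grade better and not back to own pattern |
| 13.0 | 2 weeks, tied to dose level 2 | not grade 0 |

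The rules conflict on timing and threshold and must be reconciled. Each of them takes non-improving patients out. Where the threshold is grade 0, partial responders go too.

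**Step 3: does the follow-up statement rescue the second sample?** Sections 1.0 and 4.1 say every patient is followed for 12 weeks, but neither mentions stool collection after removal. A removed patient is off colesevelam and may be on another antidiarrheal (section 9.3), so a sample at calendar week 12 would not be one taken after 12 weeks of therapy.

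**Step 4: how many pairs?** Assumption: the share retained to week 12 equals the response rate, so expected pairs = number enrolled × response rate.

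- 10% (uninteresting rate, section 14.0): 25 × 0.10 = 2.5.
- 20% (5 of 25, the smallest promising result): 25 × 0.20 = 5.
- 30% (target): 25 × 0.30 = 7.5. The binomial chance of 5 or fewer pairs is 0.19.
- Case series in section 3.0, bowel habits normalised in 5 of 10: 25 × 0.50 = 12.5.
- Same series, some improvement in 10 of 10: 25 × 1.00 = 25.

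Allowing for early stopping at 10%: the chance of stopping after stage 1 is 0.515, so expected enrolment is 16 + (1 − 0.515) × 9 = 20.4, and expected pairs are 20.4 × 0.10 = 2.0.

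If 20% of responders also left before week 12 for other reasons (an assumption; the documents give no figure), the counts with 25 enrolled at 10%, 20% and 30% become 2.0, 4.0 and 6.0.

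**Step 5: what could a sample at removal add?** At 30% response with 25 enrolled, 25 × 0.70 = 17.5 non-responders could each give a second sample, so up to 25 pairs would be possible.

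**The case against.** The strongest reply is that this is a descriptive correlative, for which a fixed 12-week interval is a defensible choice, and that several stronger criticisms a reader might infer are not supported.

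- *That the plan presents the change as an effect of colesevelam.* It does not. Section 14.0 speaks of summarising and describing changes before and after treatment, with no test and no causal claim. The fault is an unlabelled selected population.
- *That the paired group is responders only.* This is too strong. Section 14.0 counts success at any point in the first 4 weeks. A responder may later leave for toxicity, and one whose diarrhea partly returns may stay. Whether partial responders stay depends on which removal rule applies. The accurate description is patients retained to week 12.
- *That responders and non-responders cannot be compared at all.* Baseline samples can be compared, to the extent that they are collected. Only change from baseline is lost.
- *That no more than 7 or 8 pairs will exist.* The 10% and 30% are decision thresholds, not forecasts of retention. The only clinical experience in the documents points to higher numbers, although that series reported no grades and some of its patients also followed a low-fat diet.

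It is also fair to say that Table 4 has no off-study visit, and that the week 1, 2 and 4 assessments may be by telephone, so a sample at removal carries some burden. Nor does such a sample fully separate drug effect from recovery in a single-arm trial.

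All of this stands and narrows the point. It does not answer the gap itself: a promise of samples from all patients, removal rules that prevent it, and an analysis that does not mention the loss.

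**Conclusion.** The concern holds in a limited form. Following the plan as written gives an average Inverse Simpson change in patients retained to week 12, a group selected largely by response, and makes change from baseline unavailable for patients removed for non-response. The selection follows from the documents whenever some patients fail to improve; it needs no numerical assumption.

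The size of the loss does need one. With retention equal to response and 25 enrolled, expected pairs run from 2.5 (about 2 with early stopping) through 7.5 to between 12.5 and 25. If everyone improved enough to stay, there would be no loss. No single figure in this range should be quoted as the expected result.

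The importance is low. The analysis is exploratory, and the primary endpoint and its decision rule are untouched. It is worth correcting because the change is cheap and the samples cannot be obtained afterwards.

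**What to change.** 1. In sections 4.2, 8.7, 10.7 and Table 4, schedule the second research stool sample at week 12 or at the time of coming off study, whichever is first. A return kit is enough where that assessment is by telephone.
2. In section 14.0, report change by response status with time on drug shown. Keep the fixed 12-week change as a separate summary labelled 'patients retained to week 12', with the number of pairs.
3. Add a comparison of baseline microbiota (and bile acids, if measured) by response status. First reconcile section 8.3, which calls the microbiota sample optional, with sections 4.2, 8.7 and 10.7, which say all patients.
4. Reconcile the removal rules in sections 1.0, 4.1, 4.2, 9.1, 9.2, 9.3, 13.0 and Table 4 footnote b, so that it is clear who can reach week 12.

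**Cost.** No more than the two samples per patient already planned, plus a kit or drop-off for some removed patients.

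**Downsides.** Samples at removal would come at about week 2 or 4 and the others at week 12, so response status is partly confounded with time on drug. A single arm still cannot fully separate drug effect from recovery. If no collection can be added, the labelling, the pair count and the baseline comparison remain worthwhile and use material already planned.
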